5.1.2. General rule and analysis

Baseline

Unless otherwise stated, the "baseline" in this study is defined as the last non-missing measurement value obtained prior to the first use of the investigational drug, including the measurements taken on the day of and prior to the first dose.

Study days

The day of the first dose is defined as the start day of the study. Then, based on the start day of the study, the number of days of study corresponding to test or event is calculated by the following formula:

- Study days = examination date - start date of the study, if the date of an examination/event is before the start date of study;
- Study days = examination date - start date of the study + 1, if the date of an examination/event is on or after the start day of study.

General analysis

Unless otherwise specified, the following descriptive statistics will be summarized by the type of variables:

- Continuous variables will be summarized using mean, standard deviation, median, maximum, and minimum.
- Categorical variables will be summarized using frequency and percentage;
- For time-to-event variables, Kaplan-Meier method will be used to estimate the survival function and median time to event onset, and a survival curve will be plotted.

Number of decimal places

Unless otherwise specified, number of decimal places in the analysis report will be determined as per the following rules:

- The decimal places of the minimum and maximum will remain the same as that of raw data to be acquired; there should be one additional decimal place for the mean and median, and 2 additional decimal places for standard deviation, up to 4 decimal places.
- The percentage will be rounded to 2 decimal places. If the frequency is 0, the percentage is not displayed.

- The 95% CI, if being a decimal, will retain at least 2 decimal places, up to 4 decimal places.
- Time to event (in months) will be rounded to one decimal place.

Analysis software

All statistical analyses will be conducted using SAS® 9.4 or above.

5.1.3. Derived variables

Compliance (%) of subjects = (actual number of doses/scheduled number of doses) $\times 100\%$

Time from initial pathological diagnosis to enrollment (month) = (date of enrollment - date of initial pathological diagnosis + 1)/30.44

Time from final dose to enrollment (month) = (date of enrollment - last date of any previous anti-tumor therapy + 1)/30.44

Duration of drug exposure (month) = (date of last dose +14 - date of first dose + 1)/30.44

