The safety analysis will be summarized primarily using descriptive statistics. AEs, treatment-emergent AEs (TEAEs), SAEs, laboratory data, vital signs, and other data will be statistically summarized. Also, the exposure to the investigational drug (including treatment cycle, received total dose, and dose intensity) will be statistically summarized. The above data will be analyzed and summarized using Hengrui's current clinical study report standards. Such standards include but are not limited to the following:

Summary of AEs (of all causes and treatment-related);
Incidence and severity of AEs (of all causes and treatment-related);
Correlation analysis between AEs and investigational drug;
Analysis of outcomes of AEs;
Analysis of SAEs;
Descriptive statistical summary of laboratory measurements, vital sign data, and ECG data (post-baseline absolute values and post-baseline changes from baseline);
Classified summary of post-baseline vital sign data and ECG.

	
Statistical analysis of PK
 
PK analyses will be based on the PKS, and PK concentration and PK parameters will be summarized using descriptive statistics. Apart from the statistics listed in the general analysis, PK concentration and PK parameter data will be also summarized descriptively using geometric mean (GM), coefficient of variation (CV%), and geometric CV% (GCV%). In addition, for PK concentration data, average and median blood concentration-time curves (concentration-time curves) on linear scale and semi-logarithmic scale can be plotted, and individual subjects' concentration-time curves (linear scale and semi-logarithmic scale) can be plotted at the same time. If PK statistical analysis is outsourced, the statistical analysis plan provided independently by the vendor shall prevail for the specific statistical analysis and method plan.

Study Period	
Anticipated enrollment of the first subject: Jun. 2017
 
Anticipated enrollment of the last subject: Nov. 2017
 
Anticipated study end time: 24 months after the last subject receives the first administration (about Dec. 2019)

SCHEDULE OF ACTIVITIES

Item	Screening Period ^[1] (-28 days)	Treatment Cycle (14 days) ^[2]		End of Treatment ^[3]	Follow-Up Period	
		D1 of Cycle 1	D1 of Every Cycle (±3 days)		Safety Follow-Up ^[6]	Survival Follow-Up ^[22]
Enrollment Assessment						
Signing of Informed Consent	✓					
Verification of Eligibility	✓					
Demographics	✓					
Medical History	✓					

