7.1.5. Administration of investigational drug

SHR-1210: 200 mg/dose, intravenous drip infusion over 30 min (not less than 20 min and not more than 60 min) on D1 of each 2-week cycle. The treatment will continue until the occurrence of confirmed PD, intolerable toxicity, or other reasons specified in the protocol.

For Cycle 2 and subsequent cycles, the drug can be administered 3 days before or after the day of scheduled administration. Administration beyond 3 days after the scheduled dosing day will be considered as a dose delay. Subsequent dosing will be carried out based on the actual date of the previous dosing. All required examinations and evaluations must be completed prior to each dose.

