2.1. Study Design

This study adopts a multi-center, open-label, single-arm design to evaluate the efficacy and safety of SHR-1210 in patients with relapsed or refractory classic Hodgkin's lymphoma and the PK parameters of 12 subjects at the same time. Sixty subjects who meet the eligibility criteria will be enrolled and given SHR-1210 at 200 mg/dose on day 1 of each 2-week cycle, until the following condition occurs: progressive disease (PD), intolerable toxicity, or other reasons specified in the protocol. After treatment, the subjects entered the follow-up period would receive safety follow-up or survival follow-up.

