5.5.1. Extent of exposure

Duration of drug exposure and number of doses received will be summarized.

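### The SAP's drug-exposure formula counts 15 days for a 14-day cycle and sets no cap at death or data cut-off; exposure is overstated by 1 day as a rule and by at most 14 days

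*SAP*

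**What the plan says.** SAP 5.1.3 (Derived variables) gives a complete formula: "Duration of drug exposure (month) = (date of last dose +14 - date of first dose + 1)/30.44". SAP 5.5.1 says where it is used: "Duration of drug exposure and number of doses received will be summarized". This is a safety summary on the Safety Set.

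The cycle length is not in doubt. SAP 2.1 has subjects "given SHR-1210 at 200 mg/dose on day 1 of each 2-week cycle", and the treatment column of the protocol's Schedule of Activities is headed "Treatment Cycle (14 days" (the heading runs on to a closing bracket and a footnote mark).

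The day-count convention is also stated. For dates on or after the first dose, SAP 5.1.2 uses "Study days = examination date - start date of the study + 1", so both end days are counted.

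Neither SAP 5.1.3 nor SAP 5.5.1 limits the end date at death or data cut-off. Protocol 12.5.5 asks for an exposure summary and refers to the sponsor's report standards, but gives no formula for duration.

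**The concern.** The formula makes two adjustments that each add the end of the last cycle. Adding 14 days to the last-dose date already reaches day 1 of the next cycle, when the next dose would be due. The further + 1, which is right for an inclusive count between two days that both belong to the interval, then counts that day as exposure.

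Separately, the formula credits a full cycle after the last dose whatever happens next. A subject who dies, or whose data end, soon after a dose is credited with exposure after death or after the cut-off.

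At stake is the accuracy of a reported safety summary. A programmer following the text would reproduce both effects, and both always lengthen exposure.

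**Working it through.** The documents state no exposure result to reproduce, so the check is date arithmetic on the formula.

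**Inputs.** Formula and divisor 30.44: SAP 5.1.3. Cycle of 14 days: SAP 2.1 and the Schedule of Activities. Inclusive count: SAP 5.1.2.

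**Step 1: the extra day.** For n doses exactly 14 days apart, last dose − first dose = 14(n − 1).

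- SAP formula: 14(n − 1) + 14 + 1 = 14n + 1 days.
- n cycles of 14 days: 14n days.
- Difference: 1 day = 1/30.44 = 0.033 month.

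| Doses | SAP formula, days (months) | 14n, days (months) | Excess |
|---|---|---|---|
| 1 | 15 (0.493) | 14 (0.460) | 7.1% |
| 2 | 29 (0.953) | 28 (0.920) | 3.6% |
| 6 | 85 (2.792) | 84 (2.760) | 1.2% |
| 13 | 183 (6.012) | 182 (5.979) | 0.55% |
| 26 | 365 (11.991) | 364 (11.958) | 0.27% |
| 52 | 729 (23.949) | 728 (23.916) | 0.14% |

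The one-day excess does not depend on the doses being on schedule. With any dates, the formula gives last dose − first dose + 15, against last dose − first dose + 14 when the last dose is credited with one 14-day cycle.

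**Step 2: no cap.** Let death or cut-off fall j days after the last dose. From the last-dose day onward the formula credits 15 days. A capped count credits min(j + 1, 14) days. Total excess = 15 − min(j + 1, 14), which includes the day from step 1.

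| j (days after last dose) | Excess, days | Excess, months |
|---|---|---|
| 0 | 14 | 0.46 |
| 3 | 11 | 0.36 |
| 7 | 7 | 0.23 |
| 12 | 2 | 0.07 |
| 13 or more | 1 | 0.033 |

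The missing cap therefore adds something beyond the one-day error only when j is 0 to 12.

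**Step 3: average for a subject still on treatment at the cut-off.** Assume that j is uniform on 0 to 13. The excess then runs over 14, 13, …, 1, with mean (14 + 1)/2 = 7.5 days, and 7.5/30.44 = 0.25 month. Relative to 182 days (6 months) this is 7.5/182 = 4.1%. Relative to 730 days (24 months) it is 7.5/730 = 1.0%.

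**The case against.** The strongest reply is that this is a convention. No document says that exposure equals 14 days times the number of doses, and the two other durations in SAP 5.1.3 also carry a + 1. Protocol 2.2.3 reports concentrations of 4000–9000 ng/mL on day 15 after a single 3 mg/kg or fixed 200 mg dose, above the 2000 ng/mL given for receptor saturation, so day 15 is not free of drug. This does not rescue the formula. Under the SAP's own inclusive count, a 14-day cycle ends at last dose + 13, and persisting drug does not make the day the next dose is due part of the cycle already dosed.

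Other parts of the reply stand:

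- Protocol 12.5.5 refers to sponsor report standards that were not supplied and could contain a cap. SAP 5.5.1 does not cite such standards, although 5.5.2 to 5.5.4 and 5.5.6 do. The absence of a cap is shown only for the text supplied.
- The number of subjects on treatment at the cut-off is nowhere stated, so the effect on the mean or median cannot be computed.
- The uniform timing in step 3 is an assumption. From Cycle 2, "the drug can be administered 3 days before or after the day of scheduled administration", and Protocol Table 2 allows long interruptions. A subject whose last dose was 13 or more days earlier has only the one-day excess.
- The number of doses is unaffected, and the SAP also defines compliance (5.1.3) and summarizes drug use by cycle (5.3). Duration is not the only view of exposure.

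A reader might infer that exposure is materially inflated, and most of all in subjects still on treatment at the cut-off. The documents do not support that. It holds only on average and in absolute days. A death soon after a dose has the same 14-day maximum, and in relative terms the one-day error is largest after a single dose. Nor can the 4% figure be taken as the general size. Protocol section 12 places the primary analysis at 6 months after the last subject starts, but SAP Version 3.0 is dated 30 Aug 2020, after the anticipated study end of Dec 2019, and a later cut-off gives a smaller percentage.

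**Conclusion.** The rule is wrong as written, and the error is minor. The one-day excess follows directly from the stated formula, the 14-day cycle and the inclusive count, and needs no further assumption. At 0.033 month it is often invisible at one decimal place, the precision that SAP 5.1.2 sets for time to event (13 doses: 6.0 months either way), though not always (2 doses: 1.0 against 0.9).

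The missing cap matters more for individual subjects, with an upper limit of 0.46 month. Its average of 0.25 month rests on the uniform-timing assumption, and its existence rests on the supplied text being the whole rule.

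Exposure duration is descriptive. It enters no efficacy endpoint, test or sample-size calculation, and the adverse-event summaries listed in SAP 5.5.2 include no exposure-adjusted rates.

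**What to change.** Replace the formula in SAP 5.1.3 with:

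exposure (month) = [min(last dose + 13, date of death, data cut-off date) − first dose + 1]/30.44

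Without a cap this equals (last dose − first dose + 14)/30.44, that is 14n days for n on-schedule doses. The + 1 should stay and the 14 become 13. If the + 1 were dropped and the end date then capped, every capped subject would lose a day, and a subject first dosed on the cut-off date would have 0 days instead of 1.

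If the sponsor's standards already contain a cap, SAP 5.5.1 should cite it. If uncapped exposure is intended, the SAP should say so, and the extra day should still be removed.

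The cost is one line of SAP text and one line of programming. The only downside is slightly shorter reported exposure.

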5.1.4. Covariates and subgroups

This study includes the following subgroups:

- Age (≤ 45 years old and > 45 years old)
- IPS score (≤ 3 points and > 3 points)
- Baseline Disease Status (Relapsed and Refractory):
 - Relapsed: Best overall response to the last chemotherapy/transplant is CR or PR, and time from the end of chemotherapy/transplant to progression is > 6 months.
 - Refractory: 1. Best overall response to the last chemotherapy/transplant is CR, PR, or not evaluated, and time from the end of chemotherapy/transplant to progression is ≤ 6 months. Or, 2. Best overall response to the last chemotherapy/transplant is PD or SD.
 - Missing: Response to the last chemotherapy/transplant is not evaluated, and time from the end of last chemotherapy/transplant to progression is > 6 months.

5.1.5. Analysis window

Data obtained from post-baseline visits will be summarized by protocol visits shown in eCRF.

There is no need to consider whether the visit window specified by the protocol has been exceeded.

When a planned visit is missing, or one of the test items in the planned visit is missing or its results are invalid, the unplanned visit closest to the planned visit will be considered as the protocol visit. If the time of two unplanned visits is equally close to the time of planned visit, the later unplanned visit will be selected as the protocol visit. All visits in the protocol will be sorted chronologically. In addition, once an unplanned visit is defined in one protocol, it will no longer be defined in other protocols. In the analysis carried out by visits, the statistical analysis will be performed according to the planned time points in the protocol, i.e., the time points of unplanned visits do not need to be shown.

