History of Anti-Tumor Treatment	✓					
Safety Evaluation						
ECOG PS	✓	✓	✓	✓	✓	
Physical Examination ^[4]	✓	✓	✓	✓	✓	
Vital Signs ^[5]	✓	✓	✓	✓	✓	
Hematology	✓		✓	✓	✓	
Urinalysis ^[7]	✓		✓	✓	✓	
Fecal Occult Blood	✓		✓	✓	✓	
Hepatic and Renal Function ^[8]	✓		✓	✓	✓	
Blood Electrolytes ^[8]	✓		✓	✓	✓	
Coagulation Function ^[9]	✓		See Notes	✓	✓	
Thyroid Function ^[10]	✓		See Notes	✓	✓	

Compound Name: SHR-1210
 Protocol No.: SHR-1210-II-204
 Version 3.0, Version Date: 19 Jul., 2017

Item	Screening Period ^[1] (-28 days)	Treatment Cycle (14 days) ^[2]		End of Treatment ^[3]	Follow-Up Period	
		D1 of Cycle 1	D1 of Every Cycle (±3 days)		Safety Follow-Up ^[6]	Survival Follow-Up ^[22]
Fasting Blood Glucose	√		√	√	√	
Erythrocyte Sedimentation Rate	√					
LDH	√		√	√	√	
Virological Examination ^[11]	√		See Notes	√	√	
Blood HCG Test ^[12]	√	√	See Notes	√		
12-Lead ECG	√		√	√	√	
Echocardiography ^[13]	√					
Concomitant Medication/Treatment ^[18]	√	√	√	√	√	
Recording of AEs ^[19]	√	√	√	√	√	
Efficacy Evaluation						
Tumor CT or MRI Examination ^[14]	√		See Notes	See Notes	√	√
Tumor FDG-PET Examination ^[15]	√		See Notes			
Bone Marrow Aspiration and Biopsy ^[16]	√		See Notes			
IPS Score	√					
B Symptom Assessment ^[17]	√	√	See Notes	√		

Item	Screening Period ^[1] (-28 days)	Treatment Cycle (14 days) ^[2]		End of Treatment ^[3]	Follow-Up Period	
		D1 of Cycle 1	D1 of Every Cycle (±3 days)		Safety Follow-Up ^[6]	Survival Follow-Up ^[22]
PK Evaluation	√					
PK Blood Sampling ^[20]		See Notes	See Notes			
Study Treatment	√					
Injection of SHR-1210 ^[21]		√	√			
Others						
Survival Information					√	√
Subsequent Anti-Tumor Treatment					√	√

Note: In addition to the examinations and time points shown in this table, the investigators may order additional tests at any time. Test results should be entered into the "Unscheduled Tests" sheet of the eCRF.

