- [15] Tumor FDG-PET examination: Perform on D1 (± 7 days) of Weeks 17 and 25 after the start of treatment. For subjects who have not obtained two negative FDG-PET results after Week 1 and until Week 49, it is necessary to add a tumor FDG-PET examination on D1 (± 7 days) of Week 49. If it is necessary to determine whether a radiographic CR is obtained at other unscheduled FDG-PET evaluation time points after the start of treatment, the FDG-PET evaluation must be performed within 4 weeks after the CT evaluation.

- [16] Bone marrow aspiration and biopsy: The subject can start the study treatment before obtaining the bone marrow biopsy result, but the result must be recorded in the subject's CRF. Patients with bone marrow involvement at baseline require bone marrow aspiration or biopsy to confirm CR status. Bone marrow aspiration and biopsy specimens are collected within 2 weeks after the CT scan. There is no need to perform bone marrow assessment after the bone marrow aspiration and biopsy result turns negative.
- [17] B symptom assessment: including pyrexia of > 38 °C of unknown cause; night sweats; weight loss of > 10% within 6 months before the assessment. The evaluation will be conducted on D1 of Cycle 1, and every 2 cycles thereafter until the discontinuation of study treatment. In addition, the evaluation is performed when the subject obtains PR or CR for the first time; if the subject has obtained PR before CR, the evaluation should be performed again when CR is obtained.
- [18] Concomitant medication: Concomitant medications from 14 days before study treatment to 90 days after the last dose of study treatment will be collected. After the last dose, only concomitant medications for treatment-related AEs will be recorded.
- [19] AE: As per NCI CTCAE V4.03, all AEs that occur from the signing of the informed consent form to 90 days after the last dose or the start of new anti-tumor treatment should be observed and documented. From 30 days after the last dose, for non-serious AEs, only those related to the investigational drug, including AEs of special interest, will be collected. All AEs should be followed up until Grade 0-1, recovery to baseline levels, or reasonably explained (e.g., lost to follow-up or death).

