8.5. Unscheduled Visit

The following items should be documented at unscheduled visits for subjects developing AEs during the study:

- Results of relevant examinations
- AEs
- Concomitant medications

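### SAP 5.1.5 fills a missed planned result from the nearest unplanned visit at any distance, so by-visit safety summaries may be mis-timed and are probably, but not certainly, shifted toward abnormal values

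*SAP*

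**What the plan says.** SAP 5.1.5 assigns post-baseline data to the planned visits in the eCRF. If a planned visit is missing, or one of its test items is missing or invalid, "the unplanned visit closest to the planned visit will be considered as the protocol visit". Ties go to the later unplanned visit. The one restriction is on re-use: "once an unplanned visit is defined in one protocol, it will no longer be defined in other protocols". In by-visit analyses, "the time points of unplanned visits do not need to be shown".

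The protocol describes unscheduled visits in section 8.5: "The following items should be documented at unscheduled visits for subjects developing AEs during the study". The note under the Schedule of Activities is broader: "the investigators may order additional tests at any time", with results entered on a separate eCRF sheet for unscheduled tests.

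On missing data, SAP 5.1.6 covers imputation of dates and censoring of time-to-event data and leaves everything else unhandled. Protocol 12.5.3 likewise processes only missing dates, apart from censoring.

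**The concern.** Closest does not mean close. If a subject's only unplanned visit lies many cycles from the gap, the rule still uses it. The by-visit table then presents that value as belonging to the planned visit, and nothing in the table shows the substitution.

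The source of the fills matters too. A visit prompted by an adverse event is more likely than a routine visit to give an abnormal result. Protocol 7.4 adds more frequent liver-function monitoring after a Grade 2 hepatic event, and 10.2.4 adds prompt re-testing for possible drug-induced liver injury. A gap in ALT or AST could therefore be filled from a hepatic work-up in another cycle.

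At stake is the time course of laboratory and vital-sign abnormalities. Safety is a secondary objective, and in a single-arm trial no control group shares the distortion. The rule also fits poorly with the two statements that missing data other than dates are left alone.

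**Working it through.** The plan states no figure for this rule, so there is none to reproduce. The check has four steps.

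**1. Outputs exposed.** These are the summaries by planned visit: laboratory normal/abnormal shifts (SAP 5.5.3), vital signs (5.5.4), physical examination (5.5.6), and ECOG PS and B symptoms (5.5.7). Not exposed are ORR, which rests on best response; AE incidence, which is not a by-visit summary; and ECG and echocardiography, which the SAP only lists (5.5.5, 5.5.7).

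**2. How far away the fills would be.** From the documents: 14-day cycles, and one use per unplanned visit. Assumed: 25 planned Day 1 visits (Cycles 2 to 26), 5% missed at random, and a Poisson number of unplanned visits spread evenly over a year. Each gap takes the nearest unused unplanned visit. I take unplanned visits to include any unscheduled test result, since the SAP does not define the term. Simulation gives:

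| Unplanned visits per subject-year | Median distance of fill (days) | Fills more than 7 days away |
|---|---|---|
| 1 | 80 | 94% |
| 2 | 58 | 92% |
| 4 | 36 | 87% |
| 8 | 17 | 75% |

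Seven days is half a cycle. For comparison, the protocol's dosing window is narrower: "the drug can be administered 3 days before or after the day of scheduled administration". Under these assumptions mis-timing is the usual result of a fill, whatever the direction of bias.

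**3. Bias if visits are missed at random.** Let m be the share of subjects filled at a visit, pm the true abnormal rate in those subjects and pu the abnormal rate among the fills. The bias of the by-visit proportion is m × (pu − pm). None of these rates is in the documents. With m = 10% and pm = 10%, equal to the rate in observed subjects:

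- pu = 10%: 0.10 × (0.10 − 0.10) = 0
- pu = 30%: 0.10 × (0.30 − 0.10) = +2 percentage points
- pu = 50%: 0.10 × (0.50 − 0.10) = +4 points
- pu = 80%: 0.10 × (0.80 − 0.10) = +7 points

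At m = 5% these halve to 0, +1.0, +2.0 and +3.5 points. At m = 20% they double to 0, +4, +8 and +14 points.

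**4. Bias if those who miss visits are sicker.** Keep m = 10% and an abnormal rate p = 10% in observed subjects, and let pm differ. Leaving the cell empty has bias m × (p − pm).

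| pm | pu | Bias with fill | Bias with empty cell |
|---|---|---|---|
| 30% | 50% | 0.10 × (0.50 − 0.30) = +2 points | 0.10 × (0.10 − 0.30) = −2 points |
| 50% | 50% | 0 | 0.10 × (0.10 − 0.50) = −4 points |
| 50% | 30% | 0.10 × (0.30 − 0.50) = −2 points | −4 points |

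Upward bias therefore requires pu to exceed pm. That is plausible, but the documents do not establish it.

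**The case against.** The strongest reply is that the direction of bias is unknown. Protocol 8.5 says what to record when a subject with an adverse event attends; it does not confine unscheduled results to such subjects, and the Schedule note allows extra tests for any reason. Event-driven repeats also include recovered values, because "All AEs should be followed up until Grade 0-1, recovery to baseline levels, or reasonably explained". Where those who miss visits are sicker, step 4 shows that a fill can be unbiased, or less biased than an empty cell. All of this stands. It rules out saying that the summaries are biased toward abnormal values, or that the rule yields wrong values: the fills are real measurements that may belong to another time.

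A reader might also infer a very large effect. Suppose 3 of 55 observed subjects are abnormal (5.5%) and five gaps are filled, all with abnormal results: (3 + 5)/60 = 13.3%. That needs every fill to be abnormal and all five subjects to have an unused unplanned result. With 30% or 50% of the fills abnormal, the figure is (3 + 1.5)/60 = 7.5% or (3 + 2.5)/60 = 9.2%.

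A third tempting reading takes "There is no need to consider whether the visit window specified by the protocol has been exceeded" as a licence for distant substitution. In its place in SAP 5.1.5 the sentence follows the instruction to summarise by planned visit, so it more naturally means that a late planned visit keeps its label. The absence of a distance limit rests on the substitution sentence alone.

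Gaps may also be few. Scheduled items move with a delayed dose (Schedule of Activities, note 2), and required examinations must precede each dose (Protocol 7.1.5). This limits the size of the problem but does not justify an unlimited distance.

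**Conclusion.** The point holds as a minor one. SAP 5.1.5 as written can place values from other cycles into the by-visit safety summaries, unseen by the reader of the table. Mis-timing follows from the rule itself; a shift toward abnormal values is probable but not certain. With 10% of subjects filled, visits missed at random and a true rate of 10%, the shift runs from 0 to +7 percentage points as the abnormal rate among fills runs from 10% to 80%. It can be zero or negative if subjects who miss visits are sicker. Every rate here is an assumption. Only descriptive tables are exposed, abnormal laboratory results are listed in any case, and the primary endpoint is untouched.

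**What to change.** In SAP 5.1.5, allow substitution only when the unplanned result lies within half the interval to the adjacent planned assessment of that test, and otherwise leave the cell missing. For tests due every 14-day cycle this is ±7 days. For tests due every two or four cycles it is half of 28 or 56 days, that is ±14 or ±28 days.

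Report all unscheduled results in the listings and in the post-baseline CTCAE shift tables. State that those tables use the worst post-baseline grade; SAP 5.5.3 now refers only to grades before and after treatment. Reconcile 5.1.5 with SAP 5.1.6 and Protocol 12.5.3 by saying that this limited substitution is the one exception to leaving such data unhandled.

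The cost is a few sentences in the SAP, a simple programming window and fewer subjects in some by-visit cells. The cap limits mis-timing. It does not remove selection from event-driven visits inside the window, and if subjects who miss visits are sicker, an empty cell carries its own bias (step 4 of the working). Showing the number of observed and substituted values at each visit would let the reader judge both.
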